9.4.3 Analysis of the Secondary Endpoint(s)

[Aim 2: To determine the effect of iTBS on DLPFC rsfMRI establish a relationship between change in brain resting state functional connectivity and treatment effects

Hypothesis 2: Compared with sham, active TMS will result in a greater increase in correlation of the dorsal lateral prefrontal cortex (DLPFC) with limbic regions, in particular with the subgenual cingulate cortex (SGACC).

[MagPro X100 Stimulator, Cool-B65 Butterfly Coil]

Page 31 of 39

To assess the effect of active HDS-TBS on the functional connectome, we will test for differences in DLPFC-SGACC connectivity between the active- treated and sham-treated after 5 days of treatment. We will implement a linear regression model with change in connectivity score as the dependent variable, and age, gender, ATHF score, and use of psychotropic medication as covariates. We will examine the connectivity between DLPFC-SGACC, using the DLPFC stimulation site, identified on neuronavigation and an a priori defined SGACC ROI. We will follow Dosenbach et al.'s approach [14] for seed-based analyses to test resting state connectivity between these a priori ROIs. Functional connectivity analyses will be conducted by placing a seed (sphere with 5mm radius) in the DLPFC ROI. DLPFC seeds will match coordinates used for individual TMS coil placement. ROIs will be individually anatomically based and identified using anatomical masks on each participant's T1 volume aligned to each participant's rsfMRI data using Boundary Based Registration [15]. Average BOLD time-series data will be extracted from each ROI, for each participant, and used to calculate correlation coefficients for values at baseline and end of each 5-day treatment. These will be converted to individual z-scores using Fisher's transformation, yielding the indices representing RSFC between the seed and targets. We will use a linear mixed effects model to compare the pre- to post-treatment between-group change across the sham and active conditions. We expect that as in a previous study using HDS-iTBS, the anticorrelation between SGACC and DLPFC will increase following treatment.

Estimated regression coefficients will be reported, along with standard errors, associated confidence intervals, and p-values for hypothesis tests. In analyses adjusting for covariates, adjusted least squares means for treatment groups will be reported.

Little missing data is expected for the baseline and five-day treatment period. The mixed effects models used for Hypothesis 2 will use any data, partial or complete, provided by the randomized participants, and will yield valid estimates under missing-at-random assumptions.]

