9.4 Statistical Analyses

9.4.1 General Approach

[The analyses of the outcomes of Aims 1 and 2 will use linear mixed effects models for repeated measures. Outcomes will be measured at baseline and for each of the 5 days of TMS treatment. The model will incorporate baseline covariates (age, gender, ATHF score, use of psychotropic medication, handedness, head motion), along with randomized treatment assignment. The data collected to be

[MagPro X100 Stimulator, Cool-B65 Butterfly Coil]

Page 30 of 39

included in efficacy analyses (pre- and post-treatment) will be the measures of depression severity (MADRS), Antidepressant Treatment History Form (ATHF) data, psychotropic medication at baseline and resting state functional connectivity data (using DLPFC as a seed regions). If other variables are found to be related to the outcome and are imbalanced with respect to treatment assignment, we will perform additional analyses with these variables added to the model. For the continuous outcomes, data transformations will be implemented if there are substantial deviations from normality.

Effect size estimates and associated confidence intervals will be reported for all primary and secondary outcomes.

The trajectory of changes over the 5 days of treatment will be assessed with descriptive statistics and graphical displays. We will plot the mean daily changes in each score by treatment group to provide insight into the typical trajectory of treatment response. Because this is a short-term study we do not anticipate much (if any) missing data.]

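### Hypothesis 2 has two unranked models with conflicting covariates, and neither adjusts for baseline connectivity

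*Combined protocol and SAP*

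**What the plan says.** Section 9.4.3 describes the analysis of Hypothesis 2 twice. It opens with a "linear regression model with change in connectivity score as the dependent variable, and age, gender, ATHF score, and use of psychotropic medication as covariates". After describing how the connectivity scores are built, it adds: "We will use a linear mixed effects model to compare the pre- to post-treatment between-group change across the sham and active conditions". The two statements are not ranked or linked. Treatment arm is not named among the regression terms, although the comparison implies it. The covariates of the mixed model are not listed there.

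Section 9.4.1 sets the general rule: "The analyses of the outcomes of Aims 1 and 2 will use linear mixed effects models for repeated measures". Its covariates are "age, gender, ATHF score, use of psychotropic medication, handedness, head motion", described as baseline covariates and entered along with randomized arm. The missing-data paragraph that closes 9.4.3 speaks of one kind of model only: "The mixed effects models used for Hypothesis 2 will use any data, partial or complete, provided by the randomized participants".

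The connectivity values are "used to calculate correlation coefficients for values at baseline and end of each 5-day treatment", so there are two planned time points. The Schedule of Activities agrees: MRI at baseline and post stimulation, with an optional scan on Day 2 or 3. No section lists baseline connectivity as a covariate.

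The synopsis plans 34 subjects with 32 usable. Section 9.2 calls everything beyond Hypothesis 1 exploratory and says that the sample will give preliminary effect sizes for the secondary endpoints.

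**The concern.** Two unranked models for one hypothesis leave open which estimate and p-value are the planned ones, and 9.4.3 promises both estimates and p-values. The models differ in two ways that matter:

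- **Who is analysed.** A change score exists only for patients with both scans. The mixed model is said to use partial data as well.
- **What is adjusted for.** The regression has four covariates and 9.4.1 has six. The two missing ones are handedness and head motion. Head motion is the one item on the list that belongs to imaging, yet it is absent from the only covariate list written for the imaging outcome.

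The second issue is precision. A change score carries the measurement noise of both scans, and adjusting for the baseline value normally recovers part of that loss. Since the stated purpose of this endpoint is an effect size for future studies, a single well-defined and reasonably precise estimate is what the trial has to deliver.

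**Working it through.** **No planned figure to reproduce.** The documents give no power, effect size or variance for Hypothesis 2.

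**Inputs.** N=32 usable (synopsis). Assumed, because not stated: 16 per arm, two-sided alpha of 0.05, equal variances at the two scans (set to 1), and pre/post correlation r, shown from 0.3 to 0.9.

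**1. Does another section settle the choice of model?** Section 9.4.1 points to a mixed model, but it describes outcomes at baseline and on each of five treatment days. Connectivity is not measured that way. Its text therefore cannot be carried over to Aim 2 unchanged, and 9.4.3 still contains the regression.

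**2. Do the two models give the same answer?** With complete pairs, a mixed model with an unconstrained group-by-time term gives the same estimate as an unadjusted change-score comparison, and covariates entered only as main effects do not alter it. The regression adjusts the change itself for four covariates. The two results can therefore differ even with complete data, and differ further once a scan is missing.

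**3. Precision lost without baseline connectivity.**

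- Variance of a change score: 2(1−r).
- Residual variance after baseline adjustment: 1−r².
- Ratio: (1−r²)/[2(1−r)] = (1+r)/2.
- Cost of slopes: with q covariates unrelated to arm, the expected variance inflation is (N−3)/(N−3−q). Going from four to five covariates multiplies the variance by (29/24)/(29/25) = 25/24 = 1.042.
- Detectable difference at 80% power: noncentral t with standard error √(2V/16) and 26 degrees of freedom (four covariates) or 25 (five). V is the change-score variance, or the adjusted variance times 25/24. Units are SDs of a single connectivity score.

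| r (assumed) | 2(1−r) | 1−r² | Ratio | Ratio × 25/24 | Detectable difference, change score → adjusted |
|---|---|---|---|---|---|
| 0.3 | 1.40 | 0.91 | 0.65 | 0.677 | 1.22 → 1.00 |
| 0.5 | 1.00 | 0.75 | 0.75 | 0.781 | 1.03 → 0.91 |
| 0.7 | 0.60 | 0.51 | 0.85 | 0.885 | 0.80 → 0.75 |
| 0.9 | 0.20 | 0.19 | 0.95 | 0.990 | 0.46 → 0.46 |

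Read the other way, the unadjusted variance is larger by 1/0.677 − 1 = 48% at r=0.3 and by 1/0.885 − 1 = 13% at r=0.7. By step 2, the planned mixed model does not recover this unless the arms share a baseline mean.

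**4. Cost of also taking the covariate list up to six.** Six covariates plus baseline connectivity make seven. Relative to the four-covariate regression, the inflation is (29/22)/(29/25) = 25/22 = 1.136. If handedness and head motion explained nothing, the net ratios would be 0.65 × 1.136 = 0.74, 0.75 × 1.136 = 0.85, 0.85 × 1.136 = 0.97 and 0.95 × 1.136 = 1.08.

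**5. What the listed head-motion term can do.** In a simulation (5,000 runs, 16 per arm, assumed effect of motion on connectivity of 0.3 or 0.5 SD per SD of motion), a regression without any motion term was unbiased when motion did not differ by arm, with a type I error of 5.1% to 5.4%. When a 0.5 SD arm difference in motion at the second scan was imposed, the bias was 0.3 × 0.5 = 0.15 or 0.5 × 0.5 = 0.25. Adding baseline motion left that bias unchanged. Adding the change in motion removed it. This shows what the term can and cannot correct. It is not evidence that such a difference will occur.

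**The case against.** The best defence is that 9.4.1 and the missing-data paragraph of 9.4.3 both point to a mixed model, so a reasonable analyst would take that as the main analysis with head motion included. Little missing data is expected, so the two models would analyse nearly the same patients. Analysis of change scores is valid under randomization, and baseline adjustment is a matter of efficiency whose size depends wholly on an assumed r. No confirmatory claim rests on Hypothesis 2.

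Much of this stands and limits the weight of the point. It does not remove it. The regression is still written into the plan with its own covariate list, nothing calls it secondary, and the mixed model as described does not supply the baseline adjustment.

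A reader might go further and infer that motion artefact is left in the connectivity result, or that the false-positive rate is inflated. The documents do not support either:

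- Section 9.4.1 still places head motion in the Aim 2 mixed model, so the plan contradicts itself rather than clearly dropping the term.
- Under randomization, motion biases the contrast only if it differs systematically by arm, and nothing in the documents shows that it does.
- The listed term is a baseline covariate, so restoring it would not correct a difference at the second scan.
- The seed-based processing follows a cited approach that is not reproduced in the documents, so how motion is handled there cannot be judged.

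Nor is adjustment for second-scan motion a plain remedy. It is measured after randomization, and if treatment affects how still patients lie, conditioning on it changes what is estimated and can itself introduce bias.

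**Conclusion.** The point holds as an inconsistency and an efficiency loss, not as a demonstrated bias. Hypothesis 2 has two models, no ranking, covariate lists that disagree with 9.4.1, and a missing-data statement that fits only one of the models. Neither model adjusts for baseline connectivity.

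The efficiency loss is material at low to moderate r and close to nothing at r=0.9. If the covariate list also grows to six and the added terms explain nothing, the net gain is small at r=0.7 and becomes a loss of about 8% in variance at r=0.9. These sizes rest on equal variances, 16 per arm and an assumed r.

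The correction should be made before unblinding, but the consequences are limited to a secondary endpoint that section 9.2 treats as exploratory.

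**What to change.** In 9.4.3, name one main model for Hypothesis 2: post-treatment Fisher-z DLPFC-SGACC connectivity on arm and baseline connectivity, with the 9.4.1 covariates. The equivalent is a two-time-point mixed model with a common baseline mean for both arms. The mixed form keeps patients with only a baseline scan and so matches the missing-data statement. If the regression form is chosen, that statement needs rewording.

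Label the other model a sensitivity analysis. Make the covariate lists in 9.4.1 and 9.4.3 agree, and correct the description of time points in 9.4.1 for the imaging outcome.

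Add a sensitivity analysis with head motion from each scan, reported beside the main result, with a note that second-scan motion is measured after randomization.

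The cost is SAP wording and three degrees of freedom compared with the present regression (baseline connectivity, handedness, head motion). No new visits or scans are needed.

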9.4.4 Safety Analyses

[N/A]

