2.2 Background

[Li et al [3] first described the efficacy of a course of intermittent theta-burst stimulation (iTBS), a patterned form of repetitive transcranial magnetic stimulation (rTMS) over the left dorsal lateral prefrontal cortex (L-DLPFC) in patients with treatment refractory depression. In that study the degree of refractoriness was predictive of reduced efficacy, suggesting that highly refractory patients may require more TMS pulses to produce an antidepressant response. TBS has been shown to be more efficient than standard rTMS in modulating cortical excitability and multiple spaced iTBS (intermittent theta burst stimulation) sessions can be used to accelerate the treatment response. Recent work with transcranial magnetic stimulation (TMS) has shown that a rapid and sustained treatment response can be achieved by concentrating the usual 4-6 weeks of daily treatment into a high dose spaced theta burst TMS (HDS-TBS) treatment for 5 days [4]. Patients in that study were required to have failed conventional rTMS treatment and to meet deep brain stimulation inclusion criteria. However, that study only included MDD and excluded bipolar disorder. To date, there are no studies of HDS-TBS in bipolar disorder.

To demonstrate the feasibility of administering a high dose TBS protocol in our Center we recruited six patients with MDD into a pilot study using HDS-TBS according to the same parameters as will be used in the current proposal (10 treatments/day x 5 days), with the same stimulation settings. In our pilot study (IRB Protocol #834723), however, we only included participants with a diagnosis of MDD. Following treatment, patients had a mean reduction of 38.6% in depressive symptoms on the MADRS.]

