2.2.3 Clinical Adverse Event Profile

[Common mild AEs from TMS include: headache, local pain and discomfort, dizziness/nausea. Rare severe AEs from TMS include: seizures, worsening of depression, hearing loss, burns form the coil.

Other AEs include emotional discomfort during assessments, physical discomfort with MRI, anxiety or claustrophobia during MRI, worsening of depressive symptoms over time, mania symptoms and suicidality. In rare instances, severe AEs from MRI can include injury.]

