Participants will be recruited and will receive the Structured interview for Diagnostic and Statistical Manual of Mental Disorders, 5th Edition (DSM-V), the Montgomery-Asberg Depression Rating Scale (MADRS), the Young Mania Rating Scale (YMRS), the Oldfield Assessment for Handedness (handedness will be included in data analysis but is not an exclusionary criterion), and screening for dementia (MMSE >24). Following informed consent, participants will receive double blind randomization to active treatment with intensive iTBS rTMS or sham treatment. Participants will have a structural MRI, diffusion tensor MRI (DTI) and functional connectivity rs-fMRI scan. Both active and sham treatment will consist of 5 days of HDS-TBS treatment. We will optimize TMS coil positioning on an individual basis as described in individualized targeting of TMS to DLPFC target. On Day 2 or 3 of treatment, patients will have option to complete an additional MRI, contingent on availability and scheduling. At the end of each 5-day treatment patients will again receive an fMRI scan (one at pretreatment and 1 at post-treatment). Participants will also receive the Scale for Suicide Ideation (SSI), Hamilton Depression Rating Scale (HAM-D), additional validated self-report questionnaires, and neurocognitive assessment at pre and post-treatment. During each day of treatment, patients will complete MADRS, SSI, and YMRS to track progress. There are options for participants to complete visits remotely as possible (such as screening). The participant will also return for a 4 week follow up visit to complete MADRS, HAM-D, SSI, and YMRS. For the pre-treatment and post-treatment sessions, patients will be given the option to complete "The Battleship Task"; this is a computer-based cognitive task which examines how well patients are able to learn a set of shapes that are hidden on a grid. See "Schedule of Activities" in Section 12.1 for more detailed breakdown of the tasks per visit.

Patients will follow the recommended treatment course as best as possible. The protocol does allow for variability in the treatment timeline contingent on patient availability, MRI availability, and other scheduling factors. In this case, we are able to accommodate the participants who can not commit for 5 consecutive days or when one of these 5 days will fall on holiday. Thus, we will be able to complete the treatment course within 7-10 days.

Treatment Assessments

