5.2 Exclusion Criteria

[An individual who meets any of the following criteria will be excluded from participation in this study:

- No current substance abuse disorder for the past 6 months (previous substance abuse not exclusionary)
- Any psychotic disorder or current active psychotic symptoms (personality disorders not exclusionary unless in the opinion of the referring psychiatrist it would jeopardize participation)
- No dementia or other major neurological disorders
- Not having depression as primary disorder
- No major medical illness, for example metastatic cancer, end stage renal disease
- Not able to verify contact information. Participants must be able to follow through with the study & must have verified contact information and at least one verified contact
- Pregnancy. While there are no known risks to a fetus this is a new use of TMS, which has not been tested, thus pregnancy is exclusionary
- Score on YMRS greater than 12 (patients with mixed features have been shown not to respond well to TMS treatment [10])
- Rapid cycling Bipolar illness (patients with > 4 mood episodes within the past year will be excluded, as they have a higher risk of switch to mania [11])

[MagPro X100 Stimulator, Cool-B65 Butterfly Coil]

Page 20 of 39

- Any implants, conditions, or contraindications that would be deemed unsafe for TMS or MRI
- Currently using benzodiazepines (such as lorazepam) with a dose >1 mg per day or equivalent]

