8.3.5 Time Period and Frequency for Event Assessment and Follow-Up

[Safety will be assessed by monitoring and recording potential adverse effects at each study visit. Information on all adverse events will be recorded in the source documentation. To the extent possible, each adverse event or follow-up information will be evaluated by the PI. This allows site to determine relationship to treatment, expectedness, and seriousness of the event. It also allows the site to evaluate patient safety and work with the patient to a resolution.]

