10.1.5 Safety Oversight

[This is a low-risk study. Subject safety will be closely monitored. Subjects reporting side effects will be used to evaluate individual safety of iTBS. The PI will be monitoring the ongoing safety of subjects. PI is responsible for monitoring the data quality and the ongoing safety of subjects at respective site.]

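### Safety analyses are declared N/A, so any comparison of mania, suicidality or adverse events with sham would be post hoc

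*Combined protocol and SAP*

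**What the plan says.** Section 9.4.4 ("9.4.4 Safety Analyses") has a single entry, N/A. Sections 9.4.6 (interim analyses) and 9.4.7 (sub-group analyses) carry the same entry, so the natural reading is that none is planned.

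Other sections show that safety data matter here and will be collected:

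- Section 2.2.3 lists among the possible adverse events "worsening of depressive symptoms over time, mania symptoms and suicidality".
- Section 2.2 states: "To date, there are no studies of HDS-TBS in bipolar disorder".
- Section 5.2 excludes rapid cyclers, "as they have a higher risk of switch to mania".
- Section 4.1: "During each day of treatment, patients will complete MADRS, SSI, and YMRS to track progress". The Schedule of Activities (12.1) adds YMRS and SSI at screening, post-stimulation and the 4-week follow-up.
- Section 8.3.5: "Safety will be assessed by monitoring and recording potential adverse effects at each study visit". Sections 8.3.4.1 and 8.3.4.2 grade events for severity and relatedness.
- Section 10.1.5 describes the use of side-effect reports: "Subjects reporting side effects will be used to evaluate individual safety of iTBS".

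The nearest thing to a by-arm display is in 9.4.1: "We will plot the mean daily changes in each score by treatment group". It names no safety scale.

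**The concern.** By its own account the trial has no predecessor with this regimen in bipolar disorder. It will hold randomised, sham-controlled ratings of mania and suicidality, yet the plan commits to no use of them by arm.

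Three choices are therefore left open: who counts in the safety set, what counts as an event, and which rating is baseline. Each can change a small table. Section 7.1 makes stopping TMS equivalent to leaving the study, and section 7.2 replaces enrolled participants who are withdrawn. An informal account based on completers could omit the people who stopped because of mania or suicidality. Section 6.3 also leaves the study statistician unblinded, so choices made late could be made with allocation known.

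**Working it through.** **Step 1: is a by-arm safety summary specified anywhere else?** The plan gives no safety figure to reproduce, so this step compares sections.

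| Section | Content | By-arm safety summary? |
|---|---|---|
| 9.4.4 | N/A | No |
| 8.1 and 9.4.1 (efficacy data lists) | MADRS, ATHF, medication and connectivity; 8.1 adds an optional task | No; YMRS, SSI and adverse events are absent |
| 9.4.1 (plots) | Mean daily change in scores by group over the 5 treatment days | Possibly YMRS and SSI, though neither is named; cannot cover adverse events, stopping or week 4 |
| 9.4.2 | MADRS by arm | Covers worsening depression only |
| 9.4.8 | Individual listing of pre and post values | No; would also miss a transient rise on days 1 to 5 |
| 9.3 | Intention-to-treat principle | No safety population defined |
| 8.3.8 and 8.4.3 | Events shared with participants at individual and aggregate level | Aggregate, but not by arm |

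No section specifies a by-arm summary of adverse events, YMRS or SSI as a safety analysis.

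**Step 2: what could such a summary show?** Section 1.1 gives 34 subjects with 32 usable. The allocation ratio is not stated. Assuming 1:1, there are 34/2 = 17 or 32/2 = 16 per arm.

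*Zero events in one arm.* The two-sided exact 95% upper bound is 1 − 0.025^(1/n).
- n = 17: 1 − 0.025^(1/17) = 19.5%
- n = 16: 1 − 0.025^(1/16) = 20.6%

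*Chance of at least one event in an arm*, 1 − (1 − p)^n, for assumed true rates p:

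| p | n = 16 | n = 17 |
|---|---|---|
| 1% | 14.9% | 15.7% |
| 5% | 56.0% | 58.2% |
| 10% | 81.5% | 83.3% |

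*Testing is not realistic for rare events.* For k events against 0 with 17 per arm, Fisher's two-sided p is 2 × C(17,k)/C(34,k).
- k = 4: 2 × 2,380/46,376 = 0.103
- k = 5: 2 × 6,188/278,256 = 0.0445

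Five events against none are therefore needed for p < 0.05 (the same holds at 16 per arm, p = 0.0434). For illustrative true rates of 5% and 25%, Fisher power at 17 per arm is about 22%. It is obtained by summing the binomial probabilities of all outcomes with p ≤ 0.05.

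*Continuous scales.* The 95% half-width for an arm difference in YMRS or SSI at one time point is 1.96 × √(2/n) standard deviations: 0.67 SD at n = 17 and 0.69 SD at n = 16.

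A descriptive summary with intervals is feasible from the planned data. A powered test of rare events is not.

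**Step 3: is baseline defined for these scales?** The Schedule of Activities has YMRS and SSI at screening and Day 1 but not at the Enrollment/Baseline visit. It does not say whether the Day 1 rating precedes stimulation. Post-baseline is therefore undefined for any safety change score.

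**The case against.** The strongest reply is that little is lost. Both arms are rated and adverse events are recorded in both, so the results can be tabulated by arm later. Worsening depression, a named risk, is already compared through MADRS. The plots in 9.4.1 may cover YMRS and SSI. Section 9.2 treats further analyses as exploratory, section 9.4.9 allows additions, and the sample is too small to test rare events.

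Much of this stands, and it limits the point. A reader might go further in four ways that the documents do not support:

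- *That the trial cannot report comparative safety.* It can. What is missing is prespecification, and only for mania, suicidality and adverse events.
- *That individual review is the only use of safety data.* Sections 8.3.8 and 8.4.3 provide for aggregate-level sharing, sections 8.3.4.3 and 8.4.1 judge unexpectedness partly by frequency, and section 6.3 names an unblinded medical monitor. None of these is a comparison by arm.
- *That a sham comparison would check the risk statement in 2.3.3.* That statement compares the study with standard clinical TMS, and there is no standard-TMS arm.
- *That a by-arm analysis would separate treatment-emergent mania from illness course.* With 16 to 17 per arm the gain is transparent reporting; the numbers above do not promise more.

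The reply does not remove the omission. The plots give no intervals and cannot show events, stopping or week 4, and small size is a reason for intervals, not for having no plan.

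**Conclusion.** The point holds as an omission of prespecification. Section 9.4.4 declares no safety analysis, and no other section supplies a by-arm summary of mania, suicidality or adverse events. Any comparison with sham on these would be post hoc. The omission is certain from the text. How much it would affect the report depends on what the investigators later choose to tabulate.

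The size is best expressed through the zero-event case: no events in an arm would still be compatible with a true rate of up to about 19.5% (17 per arm) or 20.6% (16 per arm). These figures assume 1:1 allocation, which the documents do not state. The primary efficacy analysis is unaffected. The change should be made because it costs almost nothing.

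**What to change.** Replace N/A in 9.4.4 with a descriptive by-arm summary. Include everyone who received at least one session, by treatment received, and include those who withdrew and were replaced under 7.1 and 7.2. Report:

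1. Counts of participants with adverse events, with serious adverse events and with stopping due to adverse events, with exact 95% confidence intervals.
2. The proportion with any post-baseline YMRS above 12, with exact 95% intervals and the arm difference. Label this as exceeding the trial's entry limit, not as a diagnosed switch: section 5.2 justifies that limit by poor response in mixed features. It serves here only as an analysis threshold.
3. Mean YMRS and SSI change by arm with 95% intervals through post-stimulation and week 4. Give the number rated at each time and state that ratings after stopping are absent. Simple descriptives are preferable to a mixed model to week 4, because missingness may depend on the safety outcome itself.

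Define which rating is baseline for YMRS and SSI, and state whether the Day 1 rating precedes stimulation. Make no significance claim.

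The cost is SAP wording and a few tables, settled before unblinded data are examined. No new visits, data or staff are needed.
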